**Inclusion Criteria**

- 1) Subject must be  $\geq 18$  and  $\leq 95$  years of age
- 2) Clinical diagnosis of chronic limb-threatening ischemia, defined as any of the following clinical assessments: previous angiogram or hemodynamic evidence of severely diminished arterial inflow of the index limb (e.g.,  $ABI \leq 0.39$ ,  $TP / TcPO_2 < 30$  mm Hg) and
  - a) Rutherford Classification 5, ischemic ulceration *or*
  - b) Rutherford Classification 6, ischemic gangrene
- 3) Subject has been assessed by the Principal Investigator, reviewed by the Independent Review Committee (IRC), and determined that no conventional distal bypass, surgical or endovascular therapy for limb salvage is feasible due to either
  - a) absence of a usable pedal artery target (endovascular or surgical approach), or b) the presence of a pedal artery target with absence of a viable single-segment vein in either lower extremity or either arm that could be used for autogenous vein conduit.
- 4) Proximally, the Target In-flow Artery at the cross-over point must fall within the recommended vessel diameter ranges for the LimFlow stent graft by visual estimation.
- 5) Prior stent(s) to the infrainguinal arteries (e.g., iliac, SFA, and popliteal) are allowed.
- 6) Planned minor amputation (e.g., partial toe, ray or proximal foot/transmetatarsal) of target extremity within 30 days after the index procedure is allowed.
- 7) Subject is willing and able to sign the informed consent form.
- 8) Subject is enrolled in an acceptable wound care network and has an adequate support network to ensure that subject is compliant with medication regimen and follow-up study visits.
- 9) Prior to enrollment (7-day window), women of childbearing potential must have a negative pregnancy test.
- 10) Primary wound is stable (e.g., not rapidly deteriorating and/or showing signs of healing).
- 11) Stable glycemic control,  $HbA1C < 10\%$  ( $<269$ mg/dL)

- 12) Subjects requiring dialysis may be included, provided they meet *all* the following requirements:
- On dialysis for > 6 months
  - Autologous arteriovenous (AV) fistula or peritoneal access used for hemodialysis
  - Serum albumin  $\geq 30$  g/liter
  - BMI  $\geq 20$

### Exclusion Criteria

Subjects will be excluded from participating in this study if they meet any of the following criteria prior to initiation of the endovascular procedure:

- 1) Concomitant hepatic insufficiency, thrombophlebitis in the target limb, or non-treatable coagulation disorder within the past 90 days.
- 2) Active immunodeficiency disorder or currently receiving immunosuppressant therapy for an immunodeficiency disorder.
- 3) Prior peripheral arterial bypass procedure above or below the knee which would inhibit proximal inflow to the stent graft or interventional revascularization procedure within 30 days.
- 4) Previous major amputation of the target limb or presence of a wound requiring a free flap or absence of adequate viable tissue.
- 5) Life expectancy less than 12 months.
- 6) Documented myocardial infarction or stroke within previous 90 days.
- 7) Active infection (e.g., fever, significantly elevated WBC count  $>20.0 \times 10^9/L$ , and/or positive blood culture) at the time of the index procedure that may preclude insertion of a prosthesis or require major amputation (e.g., osteomyelitis proximal to metatarsals).
- 8) Known or suspected allergies or contraindications to aspirin or P2Y12 inhibitors, heparin, stainless steel, nitinol or contrast agent that cannot be adequately pre-treated.
- 9) Subject is currently taking anti-coagulants, which in the opinion of the investigator, interferes with the subject's ability to participate in the study (i.e., intermittent interruption of therapy for procedure may compromise subject's safety).

- 10) Lower extremity vascular disease that may inhibit the procedure and/or jeopardize wound healing (e.g., vasculitis, Buerger's disease, significant edema in the target limb, deep venous thrombus in the target vein, hyperpigmentation, or medial ulceration above the ankle).
- 11) Significant acute or chronic kidney disease with a serum creatinine of > 2.5 mg/dl in subjects not undergoing dialysis.
- 12) Severe heart failure (e.g., NYHA Class IV), which in the opinion of the investigator may compromise subject's ability to safely undergo a percutaneous procedure.
- 13) Any significant concurrent medical, psychological, or social condition, which may significantly interfere with the subject's optimal participation in the study, in the opinion of the investigator.
- 14) The subject is currently participating in another investigational drug or device study that has not completed the primary endpoint or that clinically interferes with the endpoints of this study.
- 15) Subject is unwilling, unable, or unlikely for cognitive or social reasons to comply with any of the protocol or follow-up requirements.

**Duration of Study**

Each enrolled subject will be followed for up to 3 years ( $\pm$  4 weeks) post-procedure. The primary endpoint assessments will be completed by 6 months ( $\pm$  2 weeks), and secondary endpoint assessments will be completed by 12 months ( $\pm$  1 month) post-procedure.

**Follow-Up Schedule**

Measures of safety and effectiveness will be assessed through hospital discharge, at 14 ( $\pm$  3) days, 30 ( $\pm$  7) days, at 2, 3, 6, and 9 months ( $\pm$  2 weeks), at one year ( $\pm$  4 weeks), two years ( $\pm$  4 weeks), and three years ( $\pm$  4 weeks). The study will be completed and closed after all subjects have either met a primary endpoint or completed the 3-year follow-up requirements.

**Independent Review:**

An Independent Review Committee (IRC), a Clinical Events Committee (CEC), a Data Monitoring Committee (DMC), and a Wound Core Lab will provide independent oversight per their respective charters.

## 2. Introduction and Background

Chronic limb-threatening ischemia (CLTI) is the most advanced form of peripheral arterial disease (PAD). CLTI is defined as PAD with a clinical syndrome including ischemic rest pain, nonhealing ulceration, and gangrene (Rutherford categories 4 to 6; Fontaine stages III to IV) attributable to objectively proven arterial occlusive disease. Within this definition, there is a broad spectrum of severity, from milder degrees of vascular insufficiency to “no option” situations where occlusive lesions are so complex, that currently available surgical and endovascular techniques are not sufficient and amputation is considered the only solution. Long-term prognosis for patient survival and limb loss are directly related to the extent of disease, and therapeutic choices have a profound impact on both life and limb. It is the highest risk and worst prognosis population—“no-option patients”—that LimFlow treats with deep vein arterialization.

[figure not shown]

Fig. A5. Fate of the patients presenting with chronic critical leg ischemia. CLI – critical limb ischemia.

[figure not shown]

Fig. A6. Fate of the patient with below-knee amputation.

Source: Norgren L, Hiatt WR, Dormandy JA, et al. Inter-society consensus for the management of peripheral arterial disease. *Intern Angiol.* 2007;26(2):81–157.

**Figure 1: CLI Primary Treatment and One Year Status**

 Conte MS. Bypass versus Angioplasty in Severe Ischaemia of the Leg (BASIL) and the (hoped for) dawn of evidence-based treatment for advanced limb ischemia. *J Vasc Surg.* 2010 May;51(5 Suppl):69S-75S.

 Conte MS, et al. Global vascular guidelines on the management of chronic limb-threatening ischemia. *J Vasc Surg.* Volume 69, Issue 6, 3S - 125S.e40

CLTI populations are difficult to study and many data sets are incomplete due to large lost to follow-up and death in longitudinal studies, but it is expected that there will be approximately between 500 and 1000 new cases of CLTI per million every year in the European and North American populations. The natural history of patients with CLTI is difficult to track as the majority of these patients receive some form of active treatment, with approximately half the patients undergoing some type of revascularization. Of those patients in surveys cited in the Inter-Society Consensus for the Management of Peripheral Arterial Disease, only a quarter who were actively being treated for CLTI had a positive resolution at one year, and in those patients who underwent amputation, two-year outcomes were even less promising (see Figure 1).

Considering the outcomes of amputation, limb salvage remains the primary goal of contemporary CLTI treatment. Even with the current opportunities for treatment, the therapeutic options in CLTI patients are limited: approximately 40% of the patients are not eligible for surgical or radiological revascularization, either due to the extent or location of atherosclerotic lesions or due to extensive co-morbidity. Wound healing is intractable in most CLTI patients who have reduced blood flow in the skin; therefore even with aggressive local wound care, patients with severe limb ischemia and chronic ulceration who do not or cannot undergo revascularization often progress to amputation.

Interventionalists have been aggressively trying to treat CLTI by attempting to open Chronic Total Occlusions (CTOs) or bypassing them in the sub-intimal space using such products as the Medtronic Pioneer catheter which tunnels a wire into the sub-intimal space at the CTO and then attempts to re-enter the vessel after the occlusion. Once a wire is in place, one can place a stent to provide a bypass conduit past the occlusion. More conventional approaches to treating PVD are also used in CLTI treatment once (if) a wire gets across the occlusion. These conventional methods include PTA, stenting, and, more recently, drug-coated balloons and drug-eluting stents. Less conventionally, laser treatment and atherectomy have been used.

The LimFlow approach to treating CLTI involves the concept of venous arterialization, which has been performed surgically for many years with first clinical surgical cases reported in the early 1900s.

Numerous small series of clinical trials have been published using a surgical approach and recent publications summarized this work.

---

 Guidelines for percutaneous transluminal angioplasty. Standards of Practice Committee of the Society of Cardiovascular and Interventional Radiology. *Radiology* 1990;177:619e26.



 Kum S, et al. Midterm Outcomes From a Pilot Study of Percutaneous Deep Vein Arterialization for the Treatment of No-Option Critical Limb Ischemia. *J Endovasc Ther.* 2017 Oct;24(5):619-626.

Non-randomized prospective pilot studies have been conducted with the LimFlow System in Singapore and in Europe. A non-randomized prospective pilot study and a CE Mark study have been conducted with the LimFlow System. These studies supported the CE Mark approval of the device on October 17, 2016. The subjects continue to be followed through 2 years post-procedure, and the results continue to be encouraging. Subjects were enrolled under an early feasibility (EFS) trial in the United States beginning in July 2017 and, while not statistically powered, the results are also promising.

#### 3.2 System Components

The LimFlow System consists of the following components:

- Ultrasound System
  - Transceiver
  - Control Mechanism
- Arterial/Venous Catheter Set
  - Arterial Catheter
  - Venous Catheter
  - Extension Cables (may be provided separately)
- Stent Graft System
  - Conical Stents: 3.5 & 4.0 x 5.5 x 60 mm
  - Cylindrical Stents: 5.5 x 60, 100, 150, & 200 mm
- Valvulotome

### 4. Study Overview and Methodology

LimFlow, Inc. (Sponsor) plans to conduct a clinical trial to investigate the safety and effectiveness of the LimFlow System for creating an AV connection in the Below The Knee (BTK) vascular system using an endovascular, minimally invasive approach to arterializing the pedal veins for the treatment of chronic limb-threatening ischemia (CLTI) in subjects ineligible for conventional endovascular or surgical limb salvage procedures.

#### 4.1 Study Design

A prospective, multi-center pivotal study consisting of up to 120 subjects designed to confirm the safety and effectiveness of the LimFlow System.

#### 4.2 Name of Investigational Device

LimFlow System™

---

#### 4.3 Number of Centers

Subjects may be enrolled at up to 25 sites. A complete listing of all clinical sites will be maintained by the Sponsor and will be available upon request.

#### 4.4 Study Population

The study population is comprised of subjects who are confirmed as “no option” (ineligible for conventional endovascular or surgical limb salvage procedures) by the Independent Review Committee (IRC). “No option” is defined as either a) absence of a usable pedal artery target (endovascular or surgical approach), or b) the presence of a pedal artery target with absence of a viable single-segment vein in either lower extremity or either arm that could be used for autogenous vein conduit.

#### 4.5 Number of Subjects

The study will enroll at least 60 and up to 120 subjects, based upon the planned adaptive trial design sample size re-estimation during enrollment.

#### 4.6 Loss to Follow-up Considerations

It is estimated that the overall general loss to follow-up will be 10% at the time of primary analysis, and a true loss to follow up rate <10% will incur censoring while a loss >10% will require various sensitivity analyses.

#### 4.7 Primary Endpoint

Amputation Free Survival (AFS) defined as freedom from major amputation and death at 6 months compared to a historical performance goal:

**Major Amputation:** above-ankle amputation of the index limb

*and*

**Death:** all-cause mortality

#### 4.8 Secondary Endpoints

**Primary Patency:** Defined as absence of occlusion of the endovascular intervention that is maintained without the need for additional or secondary surgical or endovascular procedures, at 30 days and 6 months.

**Primary Assisted Patency:** Defined as absence of occlusion of the endovascular intervention that is maintained with the use of additional or secondary surgical or endovascular procedures, as long as occlusion of the primary treated site has not occurred, at 30 days and 6 months.

**Secondary Patency:** Defined as absence of occlusion of the endovascular intervention that is maintained with the use of additional or secondary surgical or endovascular procedures after occlusion occurs, at 30 days and 6 months.

**Limb Salvage:** Defined as percentage of subjects with freedom from above-ankle amputation of the index limb, evaluated at 30 days, 3 and 6 months.

**Change in Rutherford Classification:** Defined as a change of one class or greater, as evaluated at 30 days, 3 and 6 months.

**Technical Success:** Defined as the successful creation of an arteriovenous fistula in the desired limb location with immediate morphological success.

**Procedural Success:** Defined as the combination of technical success, and absence of all-cause death, above-ankle amputation or clinically driven major re-intervention of the stent graft at 30 days.

**Target Wound Healing:** Defined as complete healing of the patient's target wound as evaluated at 30 days, 3, 6, 9 months, and 1 year.

**All Wound Healing:** Defined as complete healing of the patient's wounds as evaluated at 30 days, 3, 6, 9 months, and 1 year.

**All Wound Area Reduction:** Defined as reduction in area of the patient's wounds as evaluated at 30 days, 3, 6, 9 months, and 1 year.

**Freedom from Contrast-Induced Nephropathy:** Defined as subjects without acute (within 72 hours after intravenous contrast administration) impairment of renal function, measured as an absolute  $\geq 0.5$  mg/dL (44  $\mu\text{mol/L}$ ) increase compared to baseline SCr value that results in a value above the upper limit of the normal range.

**Procedure Time:** Defined as the time of the first puncture (venous or arterial) to when the last catheter is removed.

**Radiation Exposure:** Defined as patient radiation exposure (in milligray) during the procedure.

**Contrast Volume:** Defined as the total volume of contrast media (in milliliters) given during the procedure.

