##### 4.10.5 Clinical Events Committee (CEC)

The CEC will assess important endpoints of a trial and determine whether each meet protocol-specified criteria. CEC members will be independent medical professionals qualified by training and experience, with expertise in the fields of interventional cardiology, vascular surgery, and interventional radiology without conflict of interest. The CEC will operate according to a CEC Charter, which will detail the scope and purpose of the committee. A medical monitor (MM) will be responsible for training the CEC members on the protocol, the CEC Charter, and on the standard definitions and Protocol/Charter defined terms used for event adjudication. The MM will review each adverse event to determine whether it meets the criteria for adjudication.

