	Baseline and Screening (-6M to proc)	Treatment (Day 0) to Discharge	2 Weeks (+/- 3 Days)	1 Month (+/- 1 week)	2 Month (+/- 2 weeks)	3 Month (+/- 2 weeks)	6 Month (+/- 2 weeks)	9 Month (+/- 2 weeks)	1 Year (+/- 4 weeks)	2 Year (+/- 4 weeks)	3 Year (+/- 4 weeks)
Written Informed Consent	√										
Baseline imaging  that establishes pedal artery target	√										
Inclusion / Exclusion criteria, including IRC, assessment that subject is not a candidate for conventional surgical or endovascular limb salvage procedures	√										
Demographic data, medical history, medication review, physical exam, and pregnancy test (if applicable)	√										
Additional exams if required to confirm eligibility 	√										
Pedal vein assessment for case planning	√										
Review of medications / dual anti-platelet regimen 	√	√	√	√		√	√	√	√	√	√
Rutherford Classification (RCC)	√			√		√	√	√	√	√	√
WIFI Classification (ischemia measured via TcPO 2  or Toe Pressure)	√		√	√		√	√	√	√	√	√
Wound healing assessment, and photographs 	√		√	√		√	√	√	√	√	√
Wound culture, if suspected infection 	√	√	√	√		√	√	√	√	√	√
Pulse evaluation via hand-held continuous wave Doppler distal to the stent graft 		√ 	√	√		√	√	√	√	√	√
Serum Creatinine	√			√			√				
Numeric Pain Scale Rating (1-10)	√			√		√	√	√	√	√	√
Procedural angiogram  and device performance data		√									
Procedure time, defined from sheath insertion to final catheter removal		√									
Fluoroscopy and Contrast for the index procedure		√									
Device- or procedure-related AE and SAEs 		√	√	√	√	√	√	√	√	√	√
Assessment of amputation and/or re-intervention of the Stent Graft			√	√		√	√	√	√	√	√
Duplex Ultrasound Exam to assess Stent Graft patency 				√	√	√	√	√	√	√	√
All-cause mortality		√	√	√	√	√	√	√	√	√	√

 E.g., an angiogram without procedure or angiogram from a failed recanalization  
 Including an MRI, if there is suspected osteomyelitis and bypass conduit vein mapping if there is a pedal artery target and the ipsilateral saphenous vein has not been previously harvested  
 Dual antiplatelet therapy is recommended for 3 months post-procedure. At a minimum, all subjects are recommended to be started on DAPT at least one week before procedure or adequately pre-loaded with DAPT as per institution practice.  

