 TcPO2 will be measured at 2 constant points on the dorsum of the midfoot through the 12-month follow-up at sites who perform TcPO2.  
 Prior to any re-intervention of the stent graft, an angiogram/image and wound photograph should be obtained for adjudication purposes.  
 Optional; Sponsor will reimburse for culture any time there is a suspected infection.  
 Hand-held continuous wave Doppler will be performed immediately post-procedure and again between 4 and 30 hours post-procedure to assess for acute thrombosis; any findings of acute thrombosis in this time frame must be reported to the Sponsor within 24 hours of the exam.  
 Must include pre- and post-index arteriogram showing vasculature from hip to foot  
 Review of any hospitalizations or procedures involving the index limb, and/or potentially related to the device or procedure; all SAEs through 6 months. For subjects out of area or who refuse to come in for a visit, a telephone assessment should be conducted to capture as much information as possible at the time point.  
 If any LimFlow device is introduced but stent-graft implantation is either not attempted or unsuccessful, subjects will be followed for safety for 30 days with a minimum of phone calls to assess AFS.  
 May be performed at any additional non-study visit as standard of care, as indicated by clinical symptoms.

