### 5.8 Follow-up

Study subjects will be asked to undergo evaluation prior to and during the course of the clinical trial. Such tests and procedures are outlined in the Study Assessment Schedule.

Subjects should return to the clinic at 14 days (+/- 3 days), 1 month (+/- 1 week), at 2, 3, 6, and 9 months (+/- 2 weeks), and then annually (+/- 4 weeks) for up to 3 years following their endovascular procedure and the peripheral limb/wound should be assessed. For the purposes of this study, 1 “month” will equal 30 calendar days, e.g., 3 months would be equivalent to 90 days. For the purposes of this study, 1 “year” will equal 365 calendar days, e.g., 2 years would be equivalent to 730 days.

Visits or tests occurring outside of the specified date range will be considered protocol deviations. All protocol deviations, including visits outside of the protocol allowable window, will be documented and reported. Subject compliance with follow-up is critical. Lack of or incomplete follow-up may present a risk to the subject and may compromise study results. For subjects out of area or who refuse to come in for a follow-up visit, a telephone assessment should be conducted to capture as much information as possible at this time point.

Routine surveillance of the wound and index limb will be performed during each follow-up visit, in accordance with ACC/AHA 2006 Peripheral Disease Guidelines. Examinations will include assessments of pulse, pain, Rutherford Classification, WIfI Classification, wound healing status, medication regimen (antiplatelets, anticoagulants, antibiotics, and other pertinent medications that may affect wound healing) and any procedures or complications related to the index limb occurring since the last visit. In the event of a major amputation of the target limb, the LimFlow Stent Grafts may be harvested for evaluation.

The limb/wound will be photographed by trained personnel using the eKare Insight® system. Refer to the eKare Insight Training for photograph protocol. The eKare inSight digital wound management platform (eKare, Inc., Fairfax, Virginia, United States of America) will be used for photographing, scanning, and assessing wounds at screening and follow-up visits. eKare inSight will be provided to sites for use during the study by the Sponsor. eKare is ISO 13485 certified and is fully compliant with FDA 21 CFR Part 820, Part 11.

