### 7.2 Clinical Events Committee (CEC)

The Clinical Events Committee (CEC) will be responsible for the review of all device- or procedure-related adverse events and adjudication of study endpoint events according to the CEC charter. The details of the CEC objectives, scope of responsibilities, meeting schedule, record keeping, and other committee

administration details will be outlined in the CEC Charter and further agreed to by the committee members. CEC adjudicated events will be used in the analysis of study endpoint data.

The CEC will adjudicate the events related to the endpoints as listed below and all UADEs. The CEC will also review other events when requested to do so by Sponsor.

Events reviewed by the CEC:

**Outcomes Adjudication:** Reports of endpoint event components will be reviewed and adjudicated, including but not limited to:

- Target Limb amputation documented at ankle or above
- Target Limb Occlusion (via DUS and/or angiographic documentation)
- Target Limb Thrombosis (via DUS and/or angiographic documentation)
- Death
- Major and minor re-interventions of the index limb
- Contrast-induced nephropathy within 72 hours of the index procedure

The CEC will also review safety data while the study is in progress, including reports of any serious device- or procedure-related adverse events and/or any reports of device malfunction or failure.

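### Contrast-induced nephropathy is defined by creatinine within 72 hours, but no creatinine is scheduled in that window and the status of untested subjects is not stated

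*Protocol*

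**What the plan says.** **Definition.** Protocol Section 4.8, the Protocol synopsis and Section 15 define the event as "acute (within 72 hours after intravenous contrast administration) impairment of renal function". It requires a creatinine rise of at least 0.5 mg/dL over baseline to a value above the upper limit of normal. SAP Section 1 (synopsis) and SAP Section 3.2 keep the 72 hours and the 0.5 mg/dL but omit the upper-limit condition.

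**Schedule.** In Protocol Table 1 the row "Serum Creatinine" is marked at Visits 1, 4 and 7: baseline/screening, 1 month and 6 months. The cell under "Treatment (Day 0) to Discharge" is blank, and so is the 2-week cell.

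**Event route.** Protocol Section 7.2 lists "Contrast-induced nephropathy within 72 hours of the index procedure" among the outcomes that the Clinical Events Committee (CEC) adjudicates, and adds that "CEC adjudicated events will be used in the analysis of study endpoint data". Section 4.10.5 describes how cases arrive: "The MM will review each adverse event to determine whether it meets the criteria for adjudication". Section 8.5 requires potentially related adverse events and all serious ones to be reported through 6 months, and Section 10.3 lists nephropathy as anticipated.

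**Analysis.** Protocol Section 11.5.1 restricts proportions to values that are known. SAP Section 7 names this endpoint as a binary proportion at 72 hours with an exact binomial 95% interval and no hypothesis test. It gives no denominator and no rule for subjects without a value.

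**The concern.** The endpoint is a laboratory change over a short window, yet the plan does not schedule the laboratory test in that window. What remains is whatever creatinine values sites obtain for their own reasons, plus events that are noticed and reported. A rise that causes no symptoms and is never measured produces no report, so nothing reaches the CEC.

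At stake is how the reported figure is read. A high freedom rate with a tight interval would look like measured renal safety. If untested subjects are in the denominator as event-free, it shows only that few cases were reported. The two definitions add a second ambiguity, because the Protocol and SAP rates can differ on identical data.

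**Working it through.** The documents give no expected rate, power or number tested for this endpoint, so there is no stated figure to reproduce. The check has four steps.

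**1. Is any scheduled creatinine inside the window?** The Table 1 creatinine row has marks in columns 1, 4 and 7 of 11. As a check on alignment, the fluoroscopy and contrast row falls on the treatment-to-discharge visit, as it should. Section 5.8 sets the visit timing ("Subjects should return to the clinic at 14 days (+/- 3 days), 1 month (+/- 1 week" for that visit) and counts a month as 30 days.

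- Earliest scheduled post-procedure creatinine: 30 − 7 = Day 23, or 23 × 24 = 552 hours.
- Scheduled post-procedure draws inside 72 hours: 0 of 2.

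**2. Does other text add a draw?** The Table 1 footnotes, Section 5.6 (intra-operative data), Section 5.7 (post-operative) and Section 5.8 (follow-up) name no in-window creatinine. The plan does time another test to the hour: footnote 7 asks for Doppler "immediately post-procedure and again between 4 and 30 hours post-procedure to assess for acute thrombosis". A timed test in the same period was therefore feasible to specify.

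**3. How much could the denominator matter?** Let N be subjects treated, m those with an in-window value, and x cases, all found among the m.

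- Untested counted as free: (N − x)/N.
- Known values only: (m − x)/m.
- Gap: x/m − x/N = x(1/m − 1/N), which is 0 when m = N.

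The documents give neither m nor x. The rows below use N = 105 (the SAP maximum); m and x are **assumed** for illustration, with exact 95% intervals.

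| m | x | Untested = free | Known values only | Gap (points) |
|---|---|---|---|---|
| 105 | 5 | 95.2% (89.2–98.4) | 95.2% (89.2–98.4) | 0 |
| 79 | 4 | 96.2% (90.5–99.0) | 94.9% (87.5–98.6) | 1.3 |
| 52 | 5 | 95.2% (89.2–98.4) | 90.4% (79.0–96.8) | 4.9 |
| 26 | 5 | 95.2% (89.2–98.4) | 80.8% (60.6–93.4) | 14.5 |

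If no case is reported, counting untested subjects as free gives 105/105. The lower limit is 0.025^(1/105) = 96.5% whatever m is, including m = 0. That interval carries no information about how many subjects were measured.

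**4. Do the two definitions agree?** Every Protocol event satisfies the SAP definition, but a rise of at least 0.5 mg/dL that stays within the normal range is an event under the SAP only. On the same data the SAP freedom rate is therefore equal to or lower than the Protocol rate.

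**The case against.** The strongest reply has three parts.

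*An unscheduled test is not an untested subject.* Sites may check creatinine after contrast as routine. The source worksheets (Protocol Section 4.11) and the CEC Charter were not available and may already ask for such values. This stands. A reader might infer that the reported rate must be biased, either through a selected tested subset or through untested subjects counted as free. The documents do not support that: they do not show that any subject lacks a local value, and with full local testing the problem disappears.

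*Sections 7.2 and 11.5.1 do not conflict.* One says who determines event status, the other which values enter a proportion, and both can apply. This also stands, so reading them as a contradiction goes too far. Section 11.5.1, taken alone, leans towards excluding untested subjects. The remaining gap is narrower: nothing says whether the absence of a reported event, without an in-window creatinine, is a known value.

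*This is a descriptive secondary with a reporting route.* That is correct and limits the importance. It does not close the gap, because the route begins with a report. Section 8.4 even invites sites to weigh whether mild events merit reporting.

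**Conclusion.** The point holds, as a minor one. Three facts are firm on the documents: no scheduled creatinine falls within 72 hours, the status of subjects with neither a value nor a report is unstated, and the Protocol and SAP definitions differ.

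The size of any bias is unknown. Best- and worst-case freedom rates differ by (N − m)/N, which runs from 0 to 100 points as m goes from N to 0. A reader might take that span as an estimate of the error, but it only restates that m is not given. Under the illustrative assumptions (25–75% tested, 5–20% nephropathy among those tested) the two denominators differ by roughly 1 to 14 points at N = 105.

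Amputation-free survival, type I error and sample size are unaffected.

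**What to change.** 1. **One definition.** Use the same definition in both documents and settle whether the upper-limit condition applies.
2. **Retrieve local values.** Collect dated creatinine results from within 72 hours of contrast for subjects already treated.
3. **State the analysis set in SAP Section 7.** Base the estimate on subjects with a baseline and an in-window value. Say which baseline value is the reference, since Protocol Section 5.2 allows baseline data up to six months old. Say how dialysis subjects, eligible under inclusion criterion 12, are counted, and report them separately.
4. **Show what is missing.** Report the number without an in-window value, with best- and worst-case bounds for non-dialysis subjects. The tested subset may itself be selected, so the bounds belong beside the estimate.
5. **Table 1.** Add an in-window creatinine for any subjects still to be treated. At the SAP revision (after the N = 90 assessment, maximum 105; SAP Section 4) this reaches at most 105 − 90 = 15 subjects, or 15/105 = 14%, so it supplements the retrieval and cannot replace it.
6. **Fallback.** If in-window values cannot be obtained, relabel the endpoint as freedom from reported, CEC-adjudicated contrast-induced nephropathy.

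The cost is SAP and Protocol wording, one schedule entry and some laboratory retrieval, less if the worksheets already capture these values. The downside is a smaller denominator and a wider interval. The fallback costs only wording.
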